3.3.1 Safety

Thus far, AEs and laboratory abnormalities have been reported in an unblinded manner only. Analysis of the data is in progress. Overall, no safety signals have been observed in this trial. The majority of AEs have been mild injection site pain, headache, and pyrexia. A trend previously noted with the adjuvant AS01, increased frequency and severity of fever episodes post dose #2, has been seen, particularly in the youngest participants. The majority of laboratory abnormalities have been Grade 1. There have been no related SAEs noted. A more detailed description can be found in the Investigator's Brochure accompanying this submission.

3.3.2 Immunogenicity in Healthy Malian Children

Initial ELISA results have been generated for Year 1 as shown in Figure 16. ELISA assays from the pilot phase (pediatric arms, n=30 9-18 years old, n=30 5-8 years old; 1:1 randomization to Pfs230D1M-EPA/AS0, n=15/age arm and comparator, n=15/age arm; represented by group vaccine assignment) appear to have similar antibody responses to Pfs230D1M-EPA/AS01 vaccine as healthy adults receiving a similar vaccine regimen and same Pfs230D1M-EPA/AS01 vaccine dose. Also similar to what was seen in protocol #17-I-N006 (adult AS01-only study), children had significantly higher antibody titer measured by ELISA against Pfs230 compared to the control arm after only 2 doses given at 0 and 28 days. Antibody titers were also assessed after the third vaccination, and as expected, the Pfs230 vaccine arms had significantly higher titers compared to control arms, but again similar to the adult-only study (protocol #17-I-N006), the antibody titer was not significantly higher after the third vaccination compared to the second vaccination.

Pilot Participants

[figure not shown]
Pfs230D1M-EPA/AS01, 5-8 yo
Pfs230D1M-EPA/AS01, 9-18 yo
Comparator, 5-8 yo
Comparator, 9-18 yo
Day of Study

Figure 16. Pfs230 ELISA Results During Year 1 in Pilot Subjects.

Vaccinations administered on day 0, 28, 126 (black arrows). ELISA timepoints = day 0 (pre-vaccination), day 14 (14 days post dose 1), day 42 (14 days post dose 2), and day 140 (14 days post dose 3).

In an initial comparison of Pfs230 antibody responses in Pfs230D1M-EPA/AS01-vaccinated children at 12 weeks post dose #3, children who were found to have a DSF-positive feed (at least 1 mosquito with ≥1 oocyst) had a statistically significant (p<0.0001) lower Pfs230 antibody level than children with a negative DSF feed (Figure 17). No differences between DSF+ and DSF-were seen in antibody responses to Pfs230 in the comparator arm (p=0.9998).

Figure 17. Comparison of Subset of DSF Cohort (9- to 18-Year-Old Subjects) by Vaccine Arm and DSF Positivity.

Vaccinations administered on day 0, 28, 56 (black arrows).

3.3.3 Vaccine Efficacy in Healthy Malian Children

Results of vaccine efficacy have been unblinded for biostatistical purposes only. Table 6 provides the preliminary results of DSFs for Year 1 and Year 2 of the study. It is important to emphasize that these are preliminary results only.

	Vaccine Efficacy	95% CI	p value
Year 1	72%	42; 86	< 0.001
Year 2	75%	42; 89	< 0.001

Table 6. Vaccine Efficacy Based on DSFs for Year 1 and Year 2.

These preliminary efficacy results are extremely promising and support the idea that Pfs230D1M-EPA is an excellent candidate antigen for a TBV. Future plans for additional analyses of these positive DSFs include oocyst speciation, sieving analysis of Pfs230, and parasite genotyping.

3.4 EPA

Recombinant EPA is not a component of any licensed vaccines, but has been extensively studied as a carrier for polysaccharide conjugate vaccines. These include a typhoid vaccine containing 22-µg recombinant EPA tested in children as young as 2 months old (Lin, Ho et al. 2001, Thiem, Lin et al. 2011), and a shigellosis vaccine containing 75-µg recombinant EPA tested in children 1-7 years old (Ashkenazi, Passwell et al. 1999, Passwell, Ashkenazi et al. 2003, Passwell, Ashkenzi et al. 2010). No safety issues have been identified to date with the use of the recombinant EPA.

3.5 MATRIX M

Matrix-M is a saponin-based adjuvant manufactured by Novavax AB (Uppsala, Sweden). Although it is not yet fully understood how the Matrix-M adjuvant achieves its stimulatory effects, this adjuvant is known to transiently enhance the number of activated immune cells in the draining lymph nodes which may in turn lead to increased uptake and presentation of vaccine antigens to elicit a competent immune response (Reimer, Karlsson et al. 2012). Specifically, it has been shown that there is an increase of CD169+ macrophages, as well as activated dendritic cells, to the draining lymph nodes after immunization with Matrix-M adjuvanted vaccines, which may help to increase antigen presentation (Magnusson, Altenburg et al. 2018). Hence, CD169+ macrophages have previously been shown to have a role in transporting antigens to B lymphocytes by trapping them in the draining lymph node and to facilitate cross-presentation of the antigen to CD8+ T lymphocytes (Carrasco and Batista 2007, Gray and Cyster 2012). This may lead to increased humoral and cellular immune responses, manifested by cross-reactive antibodies and multi-functional CD4+ T lymphocytes (Bengtsson, Song et al. 2016, Shinde, Cai

et al. 2020). Consequently, Matrix-M has been shown to contribute to antigen dose-sparing and increased duration of humoral and cellular vaccine responses.

3.5.1 Summary of Clinical Experience with Matrix-M

The Matrix-M adjuvant technology (Bengtsson, Karlsson et al. 2013) is a promising technology which has been explored for various infectious diseases and has a good safety profile in humans (Shinde, Fries et al. 2018). To date, Matrix-M has been utilized in more than 25 clinical trials, including multiple Phase III trials (Table 7). In these studies, Matrix-M has been combined with multiple malaria vaccine candidates, influenza, COVID-19, and other disease indications. The most common dosage of Matrix-M has been 50 µg in adults, with a maximum dosage of 75 µg.

Datoo et al reported on a double-blind, randomized, controlled trial (NCT02925403) of a low-dose circumsporozoite protein-based 37 vaccine, R21, with two different doses of adjuvant, Matrix-M (25 µg and 50 µg), in 450 children aged 5-17 months in Nanoro, 38 Burkina Faso, a highly seasonal malaria transmission setting. Three vaccinations were administered at 4-week 39 intervals prior to the malaria season with a fourth dose one year later. R21/MM had a favorable safety profile and was well-tolerated. Vaccine efficacy (VE) was 74% (95% CI, 63-82) and 46 77% (95% CI, 67-84) in the low- and high-dose adjuvant groups, respectively. At 1 year, VE remained high at 47 77% (95% CI, 67-84) in the high-dose adjuvant group (Datoo, Natama et al. 2021).

Keech et al (Keech, Albert et al. 2020) published the results of a randomized, placebo-controlled, phase 1–2 trial to evaluate the safety and immunogenicity of the rSARS-CoV-2 vaccine (in 5-μg and 25-μg doses, with or without Matrix-M1 adjuvant in 131 healthy adults (NCT04368988). The vaccine, NVX-CoV2373 appeared to be safe and was shown to elicit immune responses that exceeded levels in Covid-19 convalescent serum. The addition of Matrix-M resulted in enhanced immune responses, was antigen dose–sparing, and induced a T helper 1 (Th1) response.

Shinde et al (Shinde, Bhikha et al. 2021) reported on rSARS-CoV-2 vaccine (containing 50 µg of Matrix-M) administered intramuscularly to adult subjects in South Africa (NCT04533399). Among 2,684 baseline seronegative participants (94% HIV-negative and 6% HIV-positive), predominantly mild-to-moderate COVID-19 developed in 15 participants in the vaccine group and in 29 in the placebo group (vaccine efficacy, 49.4%; 95% confidence interval [CI], 6.1 to 72.8). Among the vaccine recipients, the most common solicited systemic adverse events after the first dose and second dose were headache, muscle pain, and fatigue. The mean duration of such events was slightly longer after the second dose but generally less than 3 days.

In yet another recent example (NCT01444482), an influenza vaccine containing Matrix-M was tested in a randomized, observer-blinded, active comparator-controlled trial during the 2019-2020 influenza season (Shinde, Cho et al. 2020). In brief, 2,654 clinically stable, community-

dwelling adults ≥65 years of age were randomized to receive a single IM dose of either Matrix-M-adjuvanted quadrivalent nanoparticle influenza vaccine (qNIV) or a licensed inactivated influenza vaccine (IIV4). Local reactogenicity, primarily mild to moderate and transient pain, was higher in the qNIV group. qNIV was generally well tolerated and produced a qualitatively and quantitatively enhanced humoral and cellular immune response in older adults.

Table 7. Key Clinical Experience of Matrix-M with Various Vaccine Antigens.

NCT Number	Title	Conditions	Interventions	Characteristics	Population
NCT04201431	Safety, Immunogenicity and Efficacy of the Blood-stage Plasmodium Vivax Malaria Vaccine Candidate PvDBPII in Matrix M1	Malaria, Vivax	Biological: PvDBPII/Matrix M1	Phase 1 Phase 2	18 Years to 45 Years (Adult)
NCT01669512	Adjuvanting Viral Vectored Malaria Vaccines With Matrix M	Malaria	Biological: Low Dose Matrix M Regimen Biological: Standard Dose Matrix M Regimen	Phase 1	18 Years to 50 Years (Adult)
NCT04130282	VAC077: Safety and Immunogenicity of the Pfs25-IMX313/Matrix-M Vaccine	Malaria	• Biological: Pfs25-IMX313/ Matrix-M1	Phase 1	18 Years to 45 Years (Adult)
NCT04318002	Safety and Immunogenicity of RH5.1/ Matrix-M in Adults and Infants Living in Tanzania	Malaria	• Biological: RH5.1/Matrix-M	Phase 1	6 Months to 45 Years (Child, Adult)
NCT03896724	Safety, Immunogenicity and Efficacy of R21 Matrix-M in 5-17 Month Old Children in Nanoro, Burkina Faso	Malaria	 Biological: R21 adjuvanted with 25mcg Matrix-M Biological: R21 adjuvanted with 50mcg Matrix-M 	Phase 1 Phase 2	5 Months to 17 Months (Child)
NCT04271306	Safety, Immunogenicity and ex Vivo Efficacy of Pfs25-IMX313/Matrix-M in Healthy Volunteers in Bagamoyo, Tanzania.	Malaria	• Biological: Pfs25-IMX313 (10ug)/Matrix-M (50ug) • Biological: Pfs25-IMX313 (50ug)/Matrix-M (50ug) • Biological: Pfs25-IMX313 (50ug)/Matrix-M (50ug) & Pfs25-IMX313 (10ug)/ Matrix-M (50ug)	Phase 1	5 Years to 45 Years (Child, Adult)
NCT02572388	A Study to Assess the Safety and Immunogenicity of the Malaria Vaccine, R21, Administered With and Without Matrix-M1	Malaria	Biological: R21 Biological: Matrix-M1	Phase 1	18 Years to 50 Years (Adult)
NCT02925403	A Study to Assess the Safety and Immunogenicity of the Malaria Vaccine, R21, With Matrix-M1 Adjuvant	Malaria	Biological: R21/Matrix-M1 Other: Saline	Phase 1 Phase 2	18 Years to 45 Years (Adult)
NCT01444482	Study of Parenterally Administrated Adjuvanted Seasonal Influenza Vaccine in Healthy Elderly Volunteers	Influenza	Biological: Matrix M Biological: Seasonal influenza vaccine	Phase 1	65 Years to 75 Years (Older Adult)
NCT04611802	A Study Looking at the Efficacy, Immune Response, and Safety of a COVID-19 Vaccine in Adults at Risk for SARS-CoV-2	COVID-19	Biological: SARS-CoV-2 rS/ Matrix-M1 Adjuvant Other: Placebo	Phase 3	18 Years and older (Adult, Older Adult)
NCT04368988	Evaluation of the Safety and Immunogenicity of a SARS-CoV-2 rS Nanoparticle Vaccine With/Without Matrix-M Adjuvant	COVID-19	• Biological: SARS-CoV-2 rS - Phase 1 • Biological: SARS-CoV-2 rS/ Matrix-M Adjuvant, Days 0 and 21 - Phase 2 • And more	Phase 1 Phase 2	18 Years to 84 Years (Adult)
NCT04533399	A Study Looking at the Effectiveness and Safety of a COVID-19 Vaccine in South African Adults	COVID-19	• Biological: SARS-CoV-2 rS/ Matrix-M1 Adjuvant • Other: Placebo	Phase 2	18 Years to 84 Years (Adult)
NCT03580824	A Study to Determine if a New Malaria Vaccine is Safe and Induces Immunity Among Kenyan Adults, Young Children and Infants	Malaria	Biological: R21 in Matrix- M adjuvant vaccine	Phase 1 Phase 2	5 Months to 45 Years (Child, Adult)

NCT Number	Title	Conditions	Interventions	Characteristics	Population
NCT04583995	A Study Looking at the Effectiveness, Immune Response, and Safety of a COVID-19 Vaccine in Adults in the United Kingdom	COVID-19	Biological: SARS-CoV-2 rS/ Matrix M1-Adjuvant Other: Placebo Biological: Licensed seasonal influenza vaccine	Phase 3	18 Years to 84 Years (Adult, Older Adult)
NCT02078674	A(H7N9) VLP Antigen Dose-Ranging Study With Matrix-M1 TM Adjuvant	Influenza (Pandemic)	Biological: Monovalent Avian Influenza VLP (H7N9) Biological: Matrix-M1 TM adjuvant	Phase 1 Phase 2	18 Years to 64 Years (Adult)
NCT02300142	Rollover Trial for Placebo Subjects Previously Enrolled Into GEN-003-002 Study	Genital Herpes	 Biological: GEN-003 Vaccine (30-60µg of each antigen) Biological: Matrix-M2 Adjuvant (25-75µg) 	Phase 2	18 Years to 50 Years (Adult)
NCT01667341	Safety and Immunogenicity Study of Therapeutic HSV-2 Vaccine	Genital Herpes	Biological: GEN-003 with Matrix M-2 Biological: GEN-003	Phase 1 Phase 2	18 Years to 50 Years (Adult)
NCT03026348	Safety and Immunogenicity Study to Evaluate Single- or Two-Dose Regimens Of RSV F Vaccine With and Without Aluminum Phosphate or Matrix-M1 TM Adjuvants In Clinically-Stable Older Adults	Respiratory Syncytial Viruses	Biological: RSV F Vaccine with Aluminum Phosphate Adjuvant Biological: RSV F Vaccine Biological: Matrix-M1 Adjuvant	Phase 2	60 Years to 80 Years (Adult, Older Adult)
NCT02114060	Dose Ranging Safety and Efficacy of Therapeutic HSV-2 Vaccine	Genital Herpes	• Biological: GEN-003 Vaccine (30µg of each antigen) • Biological: Matrix-M2 Adjuvant (75µg) • And more	Phase 2	18 Years to 50 Years (Adult)
NCT03947190	A Study to Determine if New Types of Malaria Vaccines Are Safe, Effective and Lead to Immunity in Kenyan Adults	Malaria	Biological: R21/Matrix-M Biological: ChAd63/MVA METRAP Biological: intradermal injection (ID) or direct venous injection (DVI) of PfSPZ Challenge	Phase 2	18 Years to 45 Years (Adult)
NCT03293498	Evaluation of the Safety and Immunogenicity of a Recombinant Trivalent Nanoparticle Influenza Vaccine With Matrix M-1 Adjuvant (NanoFlu)	Influenza	 Biological: NanoFlu Biological: Fluzone HD - Day 0 Biological: Fluzone HD - Day 21 Other: Saline - Day 21 	Phase 1 Phase 2	60 Years and older (Adult, Older Adult)
NCT03658629	Phase 2 Dose and Formulation Confirmation of Quad-NIV in Older Adults	Influenza	Biological: NanoFlu (Quad- NIV) Other: Matrix-M Adjuvant Biological: Fluzone HD Biological:Flublok	Phase 2	65 Years and older (Older Adult)
NCT03970993	VAC 072-An Efficacy Study of R21/MM in Different Dose Schedules	Malaria	Biological: R21 Matrix-M vaccination Biological: R21 Matrix-M vaccination and CHMI	Phase 1 Phase 2	18 Years to 45 Years (Adult)
NCT02370589	Study to Evaluate the Immunogenicity and Safety of an Ebola Virus (EBOV) Glycoprotein (GP) Vaccine in Healthy Subjects	Ebola	Biological: Base Dose EBOV GP Vaccine Biological: 2-8x Base Dose EBOV GP Vaccine Biological: Matrix-M Adjuvant	Phase 1	18 Years to 50 Years (Adult)
NCT02515175	Evaluating New Formulation of Therapeutic HSV-2 Vaccine	Genital Herpes	• Biological: Matrix-M2 • Biological: GEN-003	Phase 2	18 Years to 50 Years (Adult)
NCT04120194	Phase 3 Pivotal Trial of NanoFlu™ in Older Adults	Influenza	Biological: NanoFlu Biological: Fluzone Quadrivalent	Phase 3	65 Years and older (Older Adult)
NCT04645147	Safety and Immunogenicity of an Epstein- Barr Virus (EBV) gp350-Ferritin Nanoparticle Vaccine in Healthy Adults With or Without EBV Infection	EBV	Biological: EBV gp350- Ferritin Vaccine Other: Matrix-M1	Phase 1	18 Years to 29 Years (Adult)
NCT03146403	Maintenance Dose Study of GEN-003 in Subjects With Genital Herpes Infection	Genital Herpes	• Biological: GEN-003 • Biological: Matrix-M	Phase 2	Child, Adult, Older Adult

NCT Number	Title	Conditions	Interventions	Characteristics	Population
NCT02905019	A Safety and Efficacy Study of R21 +/- ChAd63/MVA ME-TRAP	Malaria	Biological: R21 with Matrix- M1 Biological: ChAd63 ME-TRAP Biological: MVA ME-TRAP	Phase 1 Phase 2	18 Years to 45 Years (Adult)

4 Study Objectives

Primary Objective:

• To assess in African adults the safety and the reactogenicity of administration of Pfs230D1-EPA/Matrix-M (first-in-human) as compared to the rabies vaccine control

Secondary Objectives:

- To assess level of and duration of humoral immune responses as measured by ELISA titer response to Pfs230D1M after third immunization
- To assess the functional antibody response by SMFA to Pfs230D1M

Exploratory Objectives:

- To explore cellular and humoral responses to Pfs230D1M
- To analyze innate and adaptive states before and at early timepoints after vaccination by using RNA sequencing
- Estimation of interaction between host factors including but not limited to hemoglobinopathies, immune genes signatures, co-infections, and environmental, demographic, and socioeconomic characteristics and primary and secondary endpoints

5 Study Design

This is a Phase 1, dose-escalating, randomized, double-blind, comparator-controlled study designed to evaluate the safety, tolerability immunogenicity, and transmission-blocking activity of Pfs230D1M conjugate vaccine formulated on Matrix-M. Eighty adult subjects will be drawn from Sotuba, Mali and the surrounding areas. Participants will be randomized to one of the study arms (see below) to receive 1 of 3 dose levels of Pfs230D1-EPA/Matrix-M or a standard dose of comparator rabies vaccine administered as an IM injection at 3 timepoints (study days 1, 29, and 57).

Group 1: Pilot Group

- **Arm 1a** (n=5): 12.5 μg Pfs230D1-EPA/25 μg Matrix-M
- **Arm 1b** (n=5): 20 μg Pfs230D1-EPA/50 μg Matrix-M
- **Arm 1c** (n= 5): 40 μg Pfs230D1-EPA/50 μg Matrix-M
- Arm 1d (n=4): rabies vaccine (2.5 IU rabies virus antigen)

Group 2: Main Group

- **Arm 2a** (n=15): 12.5 μg Pfs230D1-EPA/25 μg Matrix-M
- **Arm 2b** (n=15): 20 μg Pfs230D1-EPA/50 μg Matrix-M
- Arm 2c (n=15): 40 μg Pfs230D1-EPA/50 μg Matrix-M
- Arm 2d (n=16): rabies vaccine (2.5 IU rabies virus antigen)

All vaccinated subjects will be followed for 12 months from the last study vaccination. Follow up will include safety and tolerability, as well as immunogenicity via ELISA and functional antibody responses via SMFA. Subjects will be monitored for patent parasitemia through 6 months after the final vaccination. See Appendix A for a detailed schedule of assessments.

5.1 Study Endpoints

Primary Endpoint:

• Incidence of local and systemic AEs and SAEs

Secondary Endpoints:

- Anti-Pfs230D1 IgG levels as measured by ELISA
- TRA/TBA of induced antibody in SMFA

Exploratory Endpoints:

- Cellular immune responses and antibody repertoire of functional antibody responses to vaccination
- RNA transcriptome quantification as detected by RNA sequencing comparing vaccinees to controls
- Host factors including but not limited to hemoglobinopathies, immune signatures, coinfections, and environmental, demographic, and socioeconomic characteristics

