3.2.1 Safety of Pfs230D1M-EPA/AS01 in Healthy Adults

Pilot Phase

In the pilot phase of the study, there was a staggered dose escalation of Pfs230D1M and Pfs25M, given individually and in combination. In the Pfs230D1M arms alone, vaccinations with the low dose of Pfs230D1M (13 μ g) and high dose of Pfs230D1M (40 μ g) were overall well-tolerated. Most of the related AEs were mild (Grade 1; 13 μ g: 23/29, 79%; 40 μ g: 42/51, 82%), with the majority being injection site pain. Laboratory abnormalities were also observed, with the majority being transient, asymptomatic Grade 1 (mild) and Grade 2 (moderate) neutropenias. As the high dose (40 μ g) of the Pfs230D1M/AS01 was determined safe and tolerable in the pilot study, it was selected to be used for the main phase of the study.

Main Phase

In the main phase of the trial, there was a full-dose arm (n=56) and a fractional-dose arm (n=61). The full-dose arm received Pfs230D1M-EPA/AS01 at 40 μg at 0, 1, 6, and 18 months. The fractional-dose arm received Pfs230D1M-EPA/AS01 at 40 μg at 0, 1, and 18 months and received a fractional dose of 8 μg of Pfs230D1M-EPA/AS01 at dose #3 at 6 months. Because there is no fractional dosing in the proposed trial, full details of the fractional dosing arm are not provided here; overall, the AE profile was similar to that of the full-dose arm, and further details can be found in the Investigator Brochure.

First 3 vaccinations: In the full-dose arm (n=56), the first three vaccinations were well tolerated with 66% (252/383) of the total AEs being mild. The most common Grade 1 AEs were injection site pain (95/252; 38%) followed by headache and malaria. Of the related Grade 2 AEs, 16/24 (67%) were injection site pain. Other related Grade 2 AEs were 2 episodes each of fever, headache, arthralgias, and neutropenia. Grade 1 injection site pain was reported in the full-dose arm in 95/168 (57%) doses, fractional-dose arm in 78/180 (43%) doses and control arm in 39/360 (11%) doses. Grade 2 injection site pain was also significantly greater in the full-dose and fractional-dose arms compared to the control. Grade 1 headaches were significantly greater in the full-dose arm than the control arm.

Booster dose: The fourth dose of Pfs230D1M-EPA/AS01 was well tolerated; most AEs were mild (Grade 1 AEs; 160/363, 44%). The most commonly reported Grade 1 AE was injection site

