5.2 Sample Size and Estimated Duration of Study

A total of 80 subjects will be vaccinated with either Pfs230D1-EPA/Matrix-M (n=60) or the rabies vaccine comparator (n=20). The last study visit will occur at Month 14 (12 months after the final immunization). Up to 150 subjects will be screened to accommodate possible screening failures.

The sample size was derived to be able to demonstrate safety, tolerability, and immunogenicity of the study vaccine as described in Section 14.1.

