14.1 Sample Size

Safety:

The arms are sufficiently sized for safety. For each dose level (n=20) in Arms 1a combined with 2a, and 1b combined with 2b, 1c combined with 2c, and 1d combined with 2d, vaccination of 20 subjects gives a power of at least **0.80** for detecting 1 or more serious or severe AEs that occur with a probability of **0.077** or more per subject (or **0.90** for an event with a probability of **0.109**).

If we combine all treated groups (arms 1a/2a, 1b/2b, 1c/2c), with a total of 60 subjects, we have **80% power** to detect 1 or more serious or severe AEs that occur with a probability of **0.026** or more per subject (or **0.90** for an event with a probability of .037).

The aforementioned calculations do not assume any historical data; they are statistical consequences of the binomial distribution.

We will compare all AE event proportions between the control arm and treated arm by Fisher's exact test.

Immunogenicity:

We plan to do a test for an overall signal with a global analysis. That is, we will combine arms 1a/2a, 1b/2b, and 1c/2c into an "any vaccination" group of n=60 and combine arms 1d and 2d into a "control" group of n=20. Using historical data from the AS01 trial, we are well powered to detect a log difference (>99.9% power) and ½ log difference (99.7% power).

Following this global test, testing specific arms is of interest. To adjust for multiplicity, we use Bonferroni corrected alpha of 0.05/3. To investigate the specific arms we conduct three tests: arms 1a/2a vs controls, arms 1b/2b vs controls, and arms 1c/2c vs controls. The controls use arms 1d and 2d. This makes each analysis n=20 vs n=20. As such, we are well powered to detect a log difference (>99.9% power) and ½ log difference (89.2% power).

These calculations were made assuming normal distributions with mean and standard deviations from the AS01 trial. 1000 simulations were run to see how often a significant result came from a Wilcoxon-Mann-Whitney test (WMW).

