Appendix B. Toxicity Tables

Local Reactogenicity Grading¹

Local Reaction to Injectable Product	Mild (Grade 1)	Moderate (Grade 2)	Severe (Grade 3)	Potentially Life Threatening (Grade 4)	
Pain at site	Does not interfere with activity	Repeated use of non-narcotic pain reliever > 24 hours or interferes with activity	Any use of narcotic pain reliever or prevents daily activity	ER visit or hospitalization	
Erythema/Redness at site ²	2.5 – 5 cm	5.1 – 10 cm	> 10 cm	Necrosis or exfoliative dermatitis	
Induration/Swelling at site ³	2.5 – 5 cm and does not interfere with activity	5.1 - 10 cm or interferes with activity	> 10 cm or prevents daily activity	Necrosis	
Bruising at site ²	2.5 – 5 cm	5.1 – 10 cm	> 10 cm	Necrosis or exfoliative dermatitis	
Pruritus at site	Does not interfere with activity	Repeated use of medication > 24 hours or interferes with activity	Prevents daily activity	ER visit or hospitalization	
Limitation of arm movement	Does not interfere with activity	Repeated use of medication > 24 hours or interferes with activity	Prevents daily activity	ER visit or hospitalization	

Abbreviations: ER, emergency room.

¹ The definitions provided in the table are modified versions taken from the FDA Guidance for Industry "Toxicity Grading Scale for Healthy Adults and Adolescent Volunteers Enrolled in Preventive Vaccine Clinical Trials" dated September 2007 and DAIDS Table for Grading the Severity of Adult and Pediatric Adverse Events version 2.1 July 2017.

² In addition to grading the measured local reaction at the greatest single diameter, the measurement should be recorded as a continuous variable.

³ Induration/Swelling should be evaluated and graded using the functional scale as well as the actual measurement.

Vital Sign AE Grading¹

Vital Signs ²	Mild (Grade 1)	Moderate (Grade 2)	Severe (Grade 3)	Potentially Life Threatening (Grade 4)
Fever ³ (°C)	38.0 – 38.4 100.4 – 101.1	38.5 – 38.9 101.2 – 102.0	39.0 – 40 102.1 – 104	> 40 > 104
(°F)	100.4 – 101.1	101.2 – 102.0	102.1 – 104	
Tachycardia - beats per minute; at rest + calm	101 – 115	116 – 130	> 130	ER visit or hospitalization for arrhythmia
Bradycardia - beats per minute ⁴ ; at rest + calm	50 – 54	45 – 49	< 45	ER visit or hospitalization for arrhythmia
Hypertension (systolic) - mm Hg; at rest + calm	141 – 150	151 – 155	> 155	ER visit or hospitalization for malignant hypertension
Hypertension (diastolic) -mm Hg; at rest + calm	91 – 95	96 – 100	> 100	ER visit or hospitalization for malignant hypertension

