Abbreviations: ER, emergency room; IV, intravenous; PO, "per os" or oral administration.

¹ The definitions provided in the table are modified versions taken from the FDA Guidance for Industry "Toxicity Grading Scale for Healthy Adults and Adolescent Volunteers Enrolled in Preventive Vaccine Clinical Trials" dated September 2007 and DAIDS Table for Grading the Severity of Adult and Pediatric Adverse Events version 2.1 July 2017.

Mali Laboratory AE Grading: Adults

Hematology and Biochemistry Values ^{1, 2}	Mild (Grade 1)	Moderate (Grade 2)	Severe (Grade 3)	Potentially Life Threatening (Grade 4)
Hemoglobin (Male) - gm/dL	9.5 - 10.3	8.0 - 9.4	6.5 - 7.9	< 6.5 and/or requiring transfusion
Hemoglobin (Female) - gm/dL	8.0 - 9.3	7.0 - 7.9	6.0 – 6.9	< 6 and/or requiring transfusion
WBC Increase - 10 ³ /μL	11.5 – 15.0	15.1 - 20.0	20.1 – 25.0	> 25.0
WBC Decrease - 10³/μL	2.5 - 3.3	1.5 - 2.4	1.0 - 1.4	< 1.0 with fever
Neutrophil/Granulocyte Decrease ³ - 10 ³ /μL	0.80 - 0.90	0.50 – 0.79	< 0.50	< 0.50 with fever
Platelets Decreased - 10 ³ /μL	100 – 110	70 – 99	25 – 69	< 25
Creatinine (Male) - µmol/L	130.00 – 150.99	151.00 – 176.99	177.00 – 221.00	> 221.00 and requires dialysis
Creatinine (Female) - µmol/L	110.00 – 132.99	133.00 – 159.99	160.00 – 215.99	> 216.00 and requires dialysis
Liver Function Tests/ALT - U/L	75.0 – 150.9	151.0 – 300.9	301.0 - 600.0	> 600.0

Abbreviations: ALT, alanine transaminase; WBC, white blood cell.

¹ The laboratory values provided in the tables serve as guidelines and are dependent upon institutional normal parameters. Institutional normal reference ranges should be provided to demonstrate that they are appropriate.

² The clinical signs or symptoms associated with laboratory abnormalities might result in characterization of the laboratory abnormalities as Potentially Life Threatening (Grade 4). For example, a low sodium value that falls within a grade 3 parameter should be recorded as a grade 4 hyponatremia event if the subject had a new seizure associated with the low sodium value.

³ Note, neutropenias are graded and followed, but based on previous experience in African populations, should be interpreted with caution since lower values are more frequently observed in people of African descent (Bain 1996, Haddy, Rana et al. 1999).

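### No analysis of laboratory values or change from baseline is planned, so a moderate fall in neutrophils (about 20%, often 30%) would probably not be shown by comparing graded AEs

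*Combined protocol and SAP*

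**What the plan says.** The primary objective (Section 4) compares safety and reactogenicity with the rabies vaccine control. Section 5.1 defines the endpoint as "Incidence of local and systemic AEs and SAEs". Section 14.1 states: "We will compare all AE event proportions between the control arm and treated arm", using Fisher's exact test. Section 14.2 adds a line listing of clinical and laboratory AEs, summaries by severity and relationship, and an optional WMW test or linear regression on the number and severity of AEs. Section 14.4.1 likewise describes the primary safety comparison as one of AE rates. No section plans a summary, shift table or test of laboratory values.

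Appendix A schedules CBC, ALT and creatinine at screening, Day -7 and Day 1 before the first dose. They are repeated at 3 and 14 days after every dose (Days 4, 15, 32, 43, 60, 71), on vaccination Days 29 and 57, and on Day 85.

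Section 3.1.1 places leukopenia and neutropenia among the most common related AEs of the Alhydrogel trial. Section 3.2.1 says of the AS01 pilot: "Laboratory abnormalities were also observed, with the majority being transient, asymptomatic Grade 1 (mild) and Grade 2 (moderate) neutropenias". On neutropenias, the laboratory table in Appendix B warns that they "should be interpreted with caution since lower values are more frequently observed in people of African descent". For erythema and bruising, note 2 of the local reactogenicity table says "the measurement should be recorded as a continuous variable".

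**The concern.** A laboratory result that moves but is not reported as an AE contributes nothing to the planned comparison with rabies vaccine. Neutrophils are the obvious case. They are the recurring laboratory finding with this antigen, and the combination with Matrix-M is first-in-human. The absolute cut-offs are hard to read in this population for three reasons:

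- Appendix B itself urges caution.
- Grade 1 starts at 0.90 while the Appendix C lower limit is 1.0, so 0.91-0.99 is abnormal but ungraded.
- Section 6.4 lets participants enter with out-of-range values up to Grade 2 at the investigator's discretion.

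All three favour each participant's own baseline as the reference. Section 14.3.1 already tests within-person change for ELISA but nothing comparable is planned for the safety laboratories. At stake is whether the trial can estimate a moderate haematological effect from blood it already draws.

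**Working it through.** **1. The plan's own safety figure.** Section 14.1 sizes each dose level "for detecting 1 or more serious or severe AEs that occur with a probability of 0.077 or more per subject", with 80% probability. From 1 - (1 - p)^n:
- n = 20: p = 0.077 gives 0.799; p = 0.109 gives 0.901.
- n = 60: p = 0.026 gives 0.794; p = 0.037 gives 0.896.

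The stated 0.80 and 0.90 reproduce. They concern seeing at least one event, not showing a difference from control.

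**2. Inputs.** The ANC reference range is 1.0-4.8 (Appendix C). Grade 1 is 0.80-0.90 (Appendix B). The groups are 60 vaccine (20 per dosage) and 20 rabies (Section 5.2). Seven post-dose draws fall within the laboratory AE window of Section 12.3: Days 4, 15, 32, 43, 60, 71 and 85. Assumed, because the documents do not give them: the range is the central 95% of a log-normal; within-person correlation (rho) is 0.4 to 0.8; the fall occurs at the 3-day draws only or at all post-dose draws; alpha is two-sided 0.05.

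**3. Distribution.** Log SD = (ln 4.8 - ln 1.0)/3.92 = 0.400. The median is sqrt(4.8) = 2.19. The single-draw probability of ANC at or below 0.90 is 1.3% with no effect, 4.8% after a 20% fall, 9.1% after 30%, 17% after 40% and 31% after 50%.

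**4. What Fisher's test needs.** With no control cases it needs 5/20 in one dosage or 12/60 pooled. With one control case it needs 7/20 or 17/60 (28%). As an upper limit, treat the seven draws as independent and let a 20% fall affect all of them: 1 - (1 - 0.048)^7 = 29% of vaccinees and 1 - (1 - 0.013)^7 = 9% of controls would have a graded result. Correlation between draws lowers both proportions.

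**5. What within-person change gives.** Take the mean of the three 3-day log values minus the mean of Day -7 and Day 1. Its variance is 0.400^2 x (1 - rho) x (1/3 + 1/2). At rho = 0.6 this is 0.0533, so the SD is 0.231. A 20% fall is ln 0.8 = -0.223.
- 60 v 20: SE = 0.231 x sqrt(1/60 + 1/20) = 0.060; z = 3.74; approximate power is Phi(3.74 - 1.96) = 96%.
- 20 v 20: SE = 0.231 x sqrt(2/20) = 0.073; z = 3.05; approximate power is Phi(3.05 - 1.96) = 86%.

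**6. Simulated power.** Ranges cover both group sizes, both timings and the correlation range. They carry Monte Carlo error of a few points.

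| True fall in ANC | Fisher, any graded neutropenia | WMW on change, 3-day draws |
|---|---|---|
| 20% | about 1-21% | about 64-100% |
| 30% | about 10-72% | at least 96% |
| 40% | about 43-99% | not the point at issue |
| 50% | about 85-100% | not the point at issue |

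The optional WMW on counts of graded results has about 2-28% power at a 20% fall. At a 30% fall, pooled, it has 18-30% (3-day draws only) or 44-79% (all draws). With no effect, the tests on change rejected in 4-6% of runs.

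**7. Sensitivity.** With only Day 4, and correlation 0.5 or 0.7, WMW on change at a 20% fall has 46-71% power (20 v 20) or 64-88% (60 v 20). The advantage is smaller but remains.

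**The case against.** The strongest reply is that AE incidence is a defensible primary endpoint for a first-in-human trial, that the stated safety sizing is correct on its own terms, and that the effect missed is small: a 20% fall takes the assumed median from 2.19 to 1.75, well inside the reference range. Earlier neutropenias were found by grading, and the AS01 full-dose arm (n = 56) had only two related Grade 2 episodes over the first three vaccinations. The power contrast also averages the very draws at which the simulated fall occurs, and no document establishes when a low point would occur. All of this stands, and it limits the point to a supportive analysis.

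Some stronger readings are tempting but unsupported:

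- A reader might infer that any vaccine-related neutrophil fall would be missed. The table shows otherwise at 40-50%.
- A reader might infer that a result counts only if it crosses an Appendix B cut-off. Section 12.3 lets investigators report other medically important abnormalities, Section 12.2 requires routine review of abnormal findings by the principal investigator, and Section 12.9 counts related Grade 3 laboratory abnormalities toward halting.
- A reader might infer that induration diameter is covered by the continuous-variable note. Note 2 is attached to erythema and bruising; induration and swelling carry note 3.
- A reader might expect a non-significant Fisher test to be reported as no haematological effect. The documents do not say so.

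The safeguards do not close the gap: none estimates a difference from rabies vaccine in values above the Grade 1 cut-off.

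**Conclusion.** The gap is real and worth closing. Laboratory data enter the planned comparison only as AEs, and no analysis of values or change is specified. Under the stated assumptions a 20% fall in ANC would probably not be shown by the graded comparison, and a 30% fall often would not, although the scheduled draws could show either. Graded cases would still be listed and reviewed, so not shown here means no significant difference between arms, not that nothing is seen. The exact powers depend on the assumed ANC spread, correlation, timing and alpha. The contrast at 20% holds throughout the ranges tried; at 30% the graded test's power varies widely. The documents report neutropenia as graded AEs and give no mean fall in neutrophils, so the calculation describes sensitivity and does not predict an effect.

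**What to change.** Add a supportive analysis to Section 14.2:

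- **Lead variable:** log ANC, as the mean of the 3-day post-dose values (Days 4, 32, 60), with the 14-day values (Days 15, 43, 71) also reported because the timing of any fall is unknown.
- **Comparison:** vaccine pooled, then each dosage, against rabies vaccine, adjusted for the mean of the Day -7 and Day 1 pre-vaccination values. Use ANCOVA, or WMW on change. Report ratios of geometric means with 95% CI.
- **Other laboratories:** change from baseline by arm for WBC, hemoglobin, platelets, ALT and creatinine, descriptively and without tests.
- **Diameters:** summarise by arm the recorded erythema and bruising measurements.

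Keep the graded AE tables and comparisons as they are. The cost is one paragraph and modest programming, with no new samples, visits or participants. The small downside is a few more estimates to interpret, limited by naming one lead variable and keeping the rest descriptive.
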